8.2.6. SpO₂

Observed SpO₂ values at each scheduled visit from randomization through Day 28 and changes from baseline will be summarized descriptively and analyzed using ANCOVA. The LS means will be presented along with the associated 95% CI within each treatment group. In comparing treatments, LS mean differences in change from baseline between treatments will be presented along with associated 95% CIs and p-values. Results will be presented in tabular and graphical formats. In the event of death within 28 days, participants will have SpO₂ imputed as the lowest clinically plausible value (60%) for analysis purposes for the time period between death and 28 days.

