## 2.2. Schedule of Events

**Table 2-1: Schedule of Events**

Assessment	Screening/ enrollment	Treatment Period							Follow-up Period										
		1 a	2	3	4	5	6	7	8	9	10	11	12	13	14 [±2]	15, 16, 17, 18, 19, 20	21 [±2]	28 [±2] or ET	45 [±3]
Study Day	-1 a																		
Written informed consent	X																		
Inclusion/exclusion criteria review	X																		
Medication history	X																		
Demographics	X																		
Medical history	X																		
Vital signs (hospitalized patients) b	X	X	X	X	X	X	X	X	X	X	X	X	X	X	X	X	X	X	X
Vital signs (outpatients) b					X		X								X			X	
Peripheral oxygen saturation (SpO 2 ) (hospitalized patients) b	X	X	X	X	X	X	X	X	X	X	X	X	X	X	X	X	X	X	X
Peripheral oxygen saturation (SpO 2 ) (outpatients) b					X		X								X			X	
Height, weight c	X																	X	
12-lead electrocardiogram d	X		X		X		X								X			X	
Physical examination e	X	X		X		X		X										X	
Neurological assessment	X	X		X		X		X										X	
Nasopharyngeal swab f	X																		
Clinical laboratory tests																			
• CBC																			
• Blood chemistry																			
• Coagulation profile																			
• Biomarkers g																			
• sPLA2 activity																			
• Urinalysis																			

Assessment	Screening/ enrollment	Treatment Period							Follow-up Period											
		-1 a	1 a	2	3	4	5	6	7	8	9	10	11	12	13	14 [±2]	15, 16, 17, 18, 19, 20	21 [±2]	28 [±2] or ET	45 [±3]
Study Day																				
Serum pregnancy test	X																	X		
PK blood sample b		X	X	X																
WHO 9-point ordinal scale	X	X	X	X	X	X	X	X	X	X	X	X	X	X	X	X	X	X	X	X
Administer study intervention i		X	X	X	X	X	X	X	X											
Concomitant medications and therapies	X	X	X	X	X	X	X	X	X	X	X	X	X	X	X	X	X	X		
Adverse events	X	X	X	X	X	X	X	X	X	X	X	X	X	X	X	X	X	X	X	X

The Day 1, 4, 7, 14, and 28 visits will be performed **in person** (either at the hospital/site or via a home health provider).

The Day 2, 3, 5, 6, 8, 9, 10, 11, 12, 13, 15, 16, 17, 18, 19, 20, 21, 45, and 60 visits for discharged participants **may be conducted by phone or via ePRO**.

Note: Participants will be assessed daily per standard of care while hospitalized.

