Abbreviations: CBC = complete blood count; COVID-19 = coronavirus disease 2019; ePRO = electronic patient-reported outcome; ET = early termination; PK = pharmacokinetic; SAE = serious adverse event; sPLA2 = secretory phospholipase 2; SpO2 = peripheral oxygen saturation; WHO = World Health Organization

- a Screening, enrollment, and Day 1 of the Treatment Period can take place on the same day if the required screening test results are available.
- b Vital signs and SpO2 will be assessed per institutional practice and recorded daily through Day 28 while hospitalized. Vital signs collection is not required prior to collection of PK blood samples, and daily vital signs may be collected before or after PK blood samples as local procedures allow.
- c Weight at all marked visits; height at screening only.
- d Initial EKG screening should be performed within 24 hours of randomization
- e Complete physical examination at Screening; targeted physical examination at subsequent visits.
- f Nasopharyngeal swab for virologic testing, if not collected within the previous 72 hours. Nucleic acid amplification test (NAAT) confirmation of COVID-19 in a sample collected < 72 hours prior to randomization is required.
- g Biomarkers will include cardiac troponin, C-reactive protein, and ferritin.
- h Pharmacokinetic samples will be drawn from all participants in Part 1, and in a subset of approximately 14 participants in Part 2, at the following timepoints:
  - Part 1 all participants: Days 1 and 3: pre-first dose and 0.5, 1, 2, 3, 4, 6, 8, and 12 hours post-first dose. Day 2: pre-morning dose.
  - Part 2 PK participants: Day 3: pre-morning dose and 0.5, 1, 2, 3, 4, 6, 8, and 12 hours post-morning dose.
  - PK samples may be drawn via a home health provider for participants who are not hospitalized.
  - The 12-hour PK samples may be omitted for participants who are not hospitalized.
  - Samples should be drawn within windows for each timepoint: ± 15 minutes for 0.5 hour timepoint, ± 30 minutes for 1, 2, 3 and 4 hour timepoints, and ± 1 hour for 6, 8 and 12 hour timepoints.
- i There are 7 complete days of treatment. Depending on initial dose administration time, the final dose may conclude on calendar day 8.

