### 10.2. Study Periods and Visits

Participants will be assessed daily per standard of care while hospitalized and on a regular basis after discharge. The Day 1, 4, 7, 14, and 28 visits will be performed in person (either at the hospital/site or via a home health provider) to assess safety, obtain blood and urine samples for laboratory tests, and obtain clinical outcome data. The Day 2, 3, 5, 6, 8, 9, 10, 11, 12, 13, 15, 16, 17, 18, 19, 20, 21, 45, and 60 visits for discharged participants may be conducted by phone or via ePRO devices.

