### **10.2.3 Follow-up Period**

#### **10.2.3.1 Days 8, 9, 10, 11, 12, and 13**

- If hospitalized, measure vital signs and SpO2 per institutional practice
- Evaluate the participant using the WHO 9-point ordinal scale
- Record concomitant medications and concomitant therapies
- Assess and record AEs

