6.1.5. Analysis Visit Windows

Visits will be analyzed as scheduled. The windows follow the Schedule of Events in the Protocol. Screening, enrollment, and Day 1 of the Treatment Period can take place on the same day if the required screening test results are available.

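### SpO2 is compared between arms at every scheduled visit, but discharged participants have no scheduled reading at 16 to 17 of the 21 visits, and the rule for filling that gap is not settled

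*SAP*

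**What the plan says.** SpO2 through Day 28 is a secondary endpoint. Under SAP 8.2.6, observed SpO2 "values at each scheduled visit from randomization through Day 28 and changes from baseline will be summarized descriptively and analyzed using ANCOVA", and LS mean differences in change from baseline are reported with 95% CIs and p-values. After a death within 28 days, SpO2 is set to 60% for the rest of that period. SAP 6.1.5 adds: "Visits will be analyzed as scheduled. The windows follow the Schedule of Events in the Protocol".

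Collection depends on where the participant is:

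- **Inpatients.** Note b to protocol Table 2-1 says that vital signs and SpO2 "will be assessed per institutional practice and recorded daily through Day 28 while hospitalized".
- **Discharged participants.** Table 2-1 has a separate outpatient SpO2 row with four marks. Protocol 10.2 says "The Day 1, 4, 7, 14, and 28 visits will be performed in person", and that the other "visits for discharged participants may be conducted by phone or via ePRO devices". The instruction for Days 8 to 13 opens "If hospitalized, measure vital signs"; Days 15 to 20 and Day 21 carry the same condition.

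For gaps not caused by death, SAP 6.1.4 looks first to contemporaneous clinical data and then falls back on LOCF. Protocol 13.1 contains that same rule and also says that primary and secondary endpoints are tabulated by an observed-cases approach.

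**The concern.** The analysis schedule is wider than the measurement schedule. At most scheduled visits a discharged participant is not due to have SpO2 taken, so the gap is built into the design and is not dropout. Discharge happens after randomisation and may depend on treatment, so who has a reading at a given visit may itself be an effect of treatment.

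The handling of these gaps could therefore drive the visit-wise differences. Carrying values forward puts earlier data under later dates. Using only what was observed leaves the sicker participants, together with deaths scored at 60%. Either could mislead the design of later trials, which is the stated use of these exploratory results.

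**Working it through.** **1. Count the visits.** Post-baseline scheduled visits through Day 28 are Days 2 to 21 (20 visits) plus Day 28, so 20 + 1 = 21.

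**2. Identify the outpatient SpO2 visits.** Column alignment in the available text of Table 2-1 is not reliable. The four outpatient marks line up with the last four ECG marks, which protocol 10.2 places on Days 4, 7, 14 and 28. These are also the post-baseline in-person visits. The day-by-day text differs: SpO2 on Day 4 (in person) is conditional on being hospitalised, while on Day 5 (phone allowed) it is unconditional.

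| Reading | Outpatient SpO2 on Days | Visits without it |
|---|---|---|
| Schedule and in-person rule | 4, 7, 14, 28 | 21 − 4 = 17 (81%) |
| Day-by-day text taken literally | 5, 7, 14, 28 | 21 − 4 = 17 (81%) |
| Both Day 4 and Day 5 counted | 4, 5, 7, 14, 28 | 21 − 5 = 16 (76%) |

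**3. What LOCF would do.** Take a participant discharged by Day 7 and then measured only on Days 7, 14 and 28. The Day 7 value fills Days 8 to 13 (6 visits) and the Day 14 value fills Days 15 to 21 (7 visits). So 13 visit-wise comparisons contain repeats of two readings from that participant, beside fresh readings from inpatients.

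**4. What observed values would do.** Discharged participants drop out of those visits, while deaths stay in at 60%. A constructed example shows the possible direction. All outcome values are assumed and the means are unadjusted; 36 per arm follows from 72 randomised 1:1. At Day 21 each arm has 3 deaths at 60%. Active has 3 inpatients at 95% and 30 discharged at 96%; placebo has 9 inpatients at 93% and 24 discharged at 96%.

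- Everyone measured: active (180 + 285 + 2,880)/36 = 92.9; placebo (180 + 837 + 2,304)/36 = 92.25. Active is slightly better.
- Inpatients plus deaths only: active (180 + 285)/6 = 77.5; placebo (180 + 837)/12 = 84.75. Active looks about 7 points worse.

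The sign reverses because more active participants went home.

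**5. How much is affected.** The documents give no discharge timing, so the median discharge day M is assumed and varied. The second column counts visits after Day M among the 17. The third assumes exponential discharge times from Day 1 and no deaths: the share lacking a reading at visit d is 1 − 2^(−(d−1)/(M−1)) at the 17 visits and 0 at the other four, averaged over 21.

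| Assumed M | Visits (of 21) where most lack a reading | Mean share of participant-visits lacking one |
|---|---|---|
| Day 4 | 15 | 67% |
| Day 7 | 13 | 53% |
| Day 9 | 11 | 46% |
| Day 10 | 10 | 43% |
| Day 14 | 7 | 34% |
| Day 21 | 0 | 25% |

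For M = Day 9 the visits are Days 10 to 13 (4) and Days 15 to 21 (7), so 11 of 21. For M = Day 10 they fall to 10, below half.

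**The case against.** The strongest reply is that SAP 8.2.6 speaks of observed values and protocol 13.1 of observed cases, so LOCF may never touch this analysis. The only imputation specific to SpO2 is the 60% after death. LOCF is in any case a fallback behind contemporaneous clinical data, and a reading that was never scheduled may not count as missing. This stands to the extent that LOCF cannot be treated as settled. It does not rescue the comparison: the observed-values reading leads to the selected subset in step 4, and a phone or ePRO contact has no required SpO2 from which to derive a value.

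Two stronger readings are tempting and not supported. A reader might infer that most visits would compare mainly carried-forward values. That needs LOCF to apply and median discharge at about Day 9 or earlier, and the documents establish neither. A reader might also infer that, if some share of participants is home by Day 10, the same share of Day 10 values are copies from Day 7 or before. That does not follow, because anyone discharged on Days 8 to 10 has daily inpatient readings after Day 7.

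The stakes are also limited. Testing is exploratory, and SpO2 is not among the key secondary endpoints listed in SAP 8.1.1. SAP Section 10 records a pause with 18 participants in Part 1 and one in Part 2, and removes p-values from Part 1 efficacy reporting. This lowers the urgency. Part 1 will still have summary statistics and confidence intervals for secondary outcomes, and the same question arises there.

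**Conclusion.** The point holds. The SAP specifies a between-arm SpO2 ANCOVA at all 21 post-baseline visits, while discharged participants have no scheduled reading at 17 of them, or 16 if Day 5 counts. The plan does not choose between LOCF and observed values, and neither gives a sound comparison at those visits.

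The visit count rests on the documents. The share of participants affected rests on assumed discharge timing and ranges from about 25% to 67% of participant-visits for median discharge between Day 21 and Day 4. The sign reversal in step 4 shows what is possible and does not predict a result.

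Tests and p-values are at issue only for Part 2 and the Combined Population; for Part 1 the ambiguity affects summaries and confidence intervals. Separately, the Day 4 and Day 5 SpO2 instructions conflict with the Schedule of Events and the in-person visit rule.

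**What to change.** In SAP 8.2.6:

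- Limit the between-arm SpO2 ANCOVA to visits at which every participant is scheduled for measurement: Days 4, 7, 14 and 28 under the schedule and the in-person rule.
- Show the other days descriptively for inpatients, labelled as such, without between-arm tests.
- State one missing-data rule for SpO2, say whether a reading that was never scheduled counts as missing, and say which rule the Part 1 summaries follow.

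In the protocol, reconcile the Day 4 text (conditional on hospitalisation) and the Day 5 text (unconditional) with Table 2-1 and the in-person rule in 10.2.

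The cost is wording in both documents. If outpatient SpO2 is collected as Table 2-1 is read here, no new measurements are needed. SAP Section 10 already foresees a protocol and SAP amendment for the Part 2 reporting of other secondary endpoints, which could carry the change. The real loss is on early days such as Days 2 and 3: most participants may still be inpatients then, and those comparisons would become descriptive.

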## 13. STATISTICS

### 13.1. Statistical Analysis

This section is a summary of the planned statistical analyses of the primary and secondary endpoints. The statistical analysis plan (SAP) with final planned analyses will be developed and finalized before database lock.

Descriptive statistical methods will be used to summarize the data from this study with confidence intervals calculated for the primary and secondary efficacy endpoints. Unless stated otherwise, the term “descriptive statistics” refers to the number of participants (n), mean, median, standard deviation, minimum, and maximum for continuous data; and frequencies and proportions for categorical data. All data collected during the study will be included in data listings.

Participants who die will have their data after death assigned as the worst possible value within a specific scale or with regard to duration or proportion as defined by the particular outcome. Participants who do not experience a particular event will not be excluded from the analysis of duration or time-to-event endpoints and will have an appropriate value assigned. Missing data for reasons other than death will, when possible, be derived from contemporaneous clinical data. If other clinical data are not available or not determinative of the outcome, data will be imputed based on the last available value (last observation carried forward).

Unless otherwise indicated, comparative statistics between treatment and control group will report point estimates, p-values, and 95% confidence intervals with the goal of understanding the clinical importance of observed effects.

This study is considered an exploratory study. Statistical tests will be interpreted in an exploratory sense only and will not be considered formal hypothesis tests.

All efficacy variables will be summarized descriptively. Primary and secondary efficacy endpoints will be tabulated according to the “Observed Cases” approach. Exploratory hypothesis testing will also be conducted for the majority of endpoints.

Part 2 efficacy summaries will be done by randomized treatment. Part 1 efficacy data will be listed only. Hypothesis testing will be evaluated in an exploratory manner in order to inform decisions about future trials.

All statistical analyses will be conducted with the SAS® System, version 9.3 or higher.

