4.1. Introduction

Data processing, tabulation of descriptive statistics, calculation of inferential statistics, and graphical representations except for PK parameter estimation will primarily use SAS (release 9.3 or later). All PK parameter estimations will use WinNonlin® version 6.4 or later. If the use of other software is warranted, the final CSR will detail what software was used for what purposes.

Continuous (quantitative) variable summaries will include the number of participants (n) with non-missing values, mean, standard deviation (SD), median, minimum, and maximum.

Categorical (qualitative) variable summaries will include the frequency and percentage of participants who are in the particular category for each possible value. In general, the denominator for the percentage calculation will be based upon the total number of participants in the study population for the treatment groups, unless otherwise specified.

The minimum and maximum will be reported with the same degree of precision (ie, the same number of decimal places) as the observed data. Measures of location (mean and median) will be reported to 1 degree of precision more than the observed data and measures of spread (SD) will be reported to 2 degrees of precision more than the observed data.

Percentages will be presented to 1 decimal place, unless otherwise specified.

Unless otherwise indicated, comparative statistics between treatment and control group will report point estimates, p-values, and 95% confidence intervals with the goal of understanding the clinical importance of observed effects.

This study is considered an exploratory study. Statistical tests will be interpreted in an exploratory sense only and will not be considered formal hypothesis tests.

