6.1.4. Handling of Dropouts or Missing Data

Withdrawn participants will not be replaced. Randomized participants withdrawn from the study may not reenter. The subject number for a withdrawn subject will not be reassigned to another subject.

Missing data for reasons other than death will, when possible, be derived from contemporaneous clinical data. If other clinical data are not available or not determinative of the outcome, data will be imputed based on the last available value (last observation carried forward).

Participants in the ITT population who experience death will have their data after death assigned as the worst possible value within a specific scale or in regard to duration or proportion as defined by the particular outcome. Participants who do not experience a particular event will not be excluded from the analysis of duration or time-to-event endpoints and will have an appropriate value assigned.

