7.4. Exposure and Compliance

IP exposure and dosing information including the number of doses and amount of IP received will be listed for each subject.

8. Efficacy Analysis

Efficacy data for Part 1 participants will be listed only, except for data from Part 1 participants that are included in the Combined Population.

For Part 2 and the Combined Population, all statistical testing for endpoints will be 2-sided and will be evaluated in an exploratory manner to inform decisions about future trials. Tests comparing treatment and control group will report point estimates, p-values, and 95% confidence intervals. In Part 2 and the Combined Population, all efficacy variables will be summarized descriptively. The primary analytic method will include adjustment for *a priori* selected covariates as described in [Section 6.1.2](#).

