9.7. Concomitant Medication

Prior and concomitant medications will be summarized by treatment group, by the number and percentage of participants taking each medication, classified using WHO Drug Dictionary (vB3 Mar2021) Anatomical Therapeutic Chemical classes (level 3) and preferred terms.

Prior medications will be presented separately from concomitant medications. Medications that started before the first administration of IP will be considered prior medications whether or not they were stopped before the first administration of IP. Any medications continuing or starting after the first administration of IP will be considered to be concomitant. If a medication starts before the first administration of IP and continues after the first administration of IP it will be considered both prior and concomitant.

10. Changes from Planned Analysis

Recruitment was paused 03May2022 due to slow enrollment following low infection rates and hospitalizations with severe severe COVID-19. At the time of this pause, Part 1 was concluded with N=18 subjects, and only one subject was recruited for Part 2. In the interest of providing results in a timely manner and informing broader medical knowledge, the decision was made to report unblinded results on Part 1 participants (N=18). It was originally specified that efficacy data for Part 1 subjects would be listed only; however, summary statistics and confidence intervals will now be reported for primary and secondary outcomes in addition to the originally specified listings. Subgroup analyses for the primary and secondary efficacy analyses will not be performed due to limited sample size. Exploratory outcomes will be listed only. Means, standard deviations, and quantiles will be reported for continuous outcomes; while counts and percentages will be reported for categorical or dichotomous outcomes. No hypothesis tests will be performed, and no P values will be reported for efficacy data of Part 1 subjects. The Part 1 ITT Population will be used for all efficacy analyses; and the Part 1 Safety Population will be used for all safety analyses. There will be no changes to the originally planned analysis of safety outcomes for Part 1 subjects. These changes are specified prior to database lock for the Part 1 subjects. Subsetting on the secondary outcomes described in 8.2.4 and 8.2.5 will be removed in this analysis of Part 1

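### Scoring deaths as 60% in the SpO2 means and ANCOVA makes estimates at visits after a death depend largely on the chosen value and the death count

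*SAP*

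**What the plan says.** SAP 8.2.6 states that SpO2 values at scheduled visits through Day 28, and their changes from baseline, "will be summarized descriptively and analyzed using ANCOVA". The output is LS means, LS mean differences, 95% CIs and p-values. After a death, SpO2 is "imputed as the lowest clinically plausible value (60%) for analysis purposes for the time period between death and 28 days".

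This applies a general rule. Protocol 13.1 says: "Participants who die will have their data after death assigned as the worst possible value within a specific scale". SAP 6.1.4 repeats it for the ITT population. No source or distribution is given for 60%.

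The sensitivity analyses in SAP 8.1.1 cover the primary endpoint and four key secondary endpoints: days of oxygen support, ICU days, the WHO scale and mortality. SpO2 is not among them. Those analyses vary covariates and strata, not the value given to deaths.

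SAP section 10 records the recruitment pause, with 18 participants in Part 1 and one in Part 2. For the Part 1 report it plans confidence intervals and says: "Means, standard deviations, and quantiles will be reported for continuous outcomes". It rules out efficacy tests and p-values for Part 1.

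**The concern.** Death has a natural place on most of the other scales in the plan. On the WHO scale it is the top score, 8. For day counts it takes the limit of the 28-day window. SpO2 has no such endpoint at 60%, so the number is a choice, and a least-squares model is sensitive to that choice. The gap between survivors and 60% multiplies the difference in deaths and goes straight into the LS mean difference. It also inflates the residual SD.

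The SpO2 result at later visits could therefore be mainly a mortality result in arbitrary units, although mortality is already analysed in SAP 8.2.2. A moderate difference in survivors' oxygenation would be hard to detect in that analysis. In a Part 1 arm of five or three, one death would dominate the mean and SD.

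**Working it through.** **Inputs from the documents.** Death value 60% (SAP 8.2.6). Part 2: 72 participants at 1:1, so 36 per arm. Part 1: 18 participants at 5:5:5:3 (both SAP 3.2). Testing is two-sided (SAP section 8). A 0.05 level is assumed from the 95% CIs. The plan has no power calculation, so there is no figure of its own to reproduce.

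**Assumptions, not in the documents.** Survivors' SpO2 mean near 95% with SD 2 to 3; mortality by the visit analysed of 3% to 15% per arm; a true benefit of 2 points in survivors.

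**Shift per net death, 36 per arm.** (95 − value) / 36:
- 60%: 35/36 = 0.97 points
- 50%: 45/36 = 1.25 points
- 70%: 25/36 = 0.69 points

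**Spread.** With mortality q and survivor SD s, SD = √[(1 − q)s² + q(1 − q)·35²].
- One death per arm (q = 1/36), s = 3: √(8.75 + 33.08) = 6.5. The deaths supply 33.08/41.83 = 79% of the variance.
- Same, s = 2: √(3.89 + 33.08) = 6.1.
- q = 0.10, s = 3: √(8.10 + 110.25) = 10.9. The SE of the difference is 10.9 × √(2/36) = 2.56 points, against 3 × √(2/36) = 0.71 with no deaths. The expected difference is 2 × 0.9 = 1.8 points, or 0.70 SE, which gives power of about 0.11.

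**Simulation.** ANCOVA on change from baseline, 36 per arm, baseline as covariate (correlation 0.4), values capped at 100%, 1,500 runs per case. The comparator is a Wilcoxon rank test with deaths ranked worst. Power for the 2-point survivor benefit, equal mortality in both arms:

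| Mortality per arm | ANCOVA with 60%, SD 2 | Rank test, SD 2 | ANCOVA with 60%, SD 3 | Rank test, SD 3 |
|---|---|---|---|---|
| 3% | 0.37 | 0.96 | 0.31 | 0.72 |
| 5% | 0.22 | 0.96 | 0.20 | 0.67 |
| 10% | 0.12 | 0.90 | 0.09 | 0.55 |
| 15% | 0.08 | 0.79 | 0.08 | 0.48 |

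With no deaths the ANCOVA has power 1.00 (SD 2) or 0.84 (SD 3). With exactly one death per arm it has 0.01 or 0.02.

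**Unequal deaths.**
- Three treated and one placebo death, true benefit 2 points: the ANCOVA estimate averages about −0.2.
- No treated and three placebo deaths, same benefit: power is 0.97 or more, but the estimate is 4.7 to 4.9 points, mostly mortality.
- No SpO2 effect in survivors, no treated and five placebo deaths: p < 0.05 in 79% (SD 3) to 91% (SD 2) of runs.

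**Type I error.** With equal mortality and no SpO2 effect, rejection rates are about 0.03 to 0.06.

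**Part 1, one death, survivors at 95 with SD 3.**
- Arm of five: mean (4 × 95 + 60)/5 = 88. Sum of squares 4 × 7² + 28² + 3 × 3² = 1,007; SD √(1,007/4) = 15.9; SE 7.1. The 95% CI is 88 ± 2.776 × 7.1, about 68 to 108%.
- Placebo arm of three: mean (2 × 95 + 60)/3 = 83.3, and by the same steps a CI of about 33 to 134%.

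Both intervals pass 100%, which SpO2 cannot.

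**Chance that the rule is never used.** No deaths among 72: 0.11 at 3% mortality and 0.02 at 5%. Among 18: 0.58 and 0.40; at 10% and 15%, 0.15 and 0.05.

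**The case against.** A reader might infer that the rule hides any real oxygenation effect from the whole trial. The documents do not support that. SAP 9.4 separately summarises actual SpO2 values and mentions no imputation for death. Section 10 reports quantiles for Part 1, and one death in an arm of five leaves the median at a survivor's value. Collected data are listed, and protocol 13.1 plans an observed-cases tabulation. The loss is confined to the imputed means and ANCOVA.

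A reader might also apply the power figures to the report now planned, or to every visit. Neither follows. Part 1 has no efficacy tests, and Part 2 stopped at one participant. Imputation starts only at death, so early visits carry only the deaths so far.

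Other points also stand. The survivor SD and mortality are assumed. The power table takes equal mortality and a benefit seen only in survivors; when deaths fall mainly on placebo, ANCOVA power is high. The simulation adjusts for baseline SpO2 only, and its comparator is an unadjusted rank test. The study is exploratory, and a prespecified worst value for death is a legitimate composite approach.

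What these points leave untouched is that 60% has no stated basis, enters a least-squares model directly, and is never varied. Section 6.1.4 applies the death rule to the ITT population, which section 10 uses for Part 1 efficacy. The natural reading is therefore that the Part 1 means include it, although 8.2.6 also calls the summarised values observed.

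**Conclusion.** The concern holds in a limited form. If deaths occur, the SpO2 difference, SD and CI at later visits depend largely on the chosen value and the difference in deaths. The size is 0.97 points per net death at 36 per arm, assuming survivors near 95%.

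For Part 2 and the Combined Population, should enrolment resume, last-visit power for a 2-point survivor benefit is about 0.08 to 0.37, against 0.48 to 0.96 with ranking. Those ranges rest on survivor SDs of 2 to 3 and equal mortality of 3 to 15%. False positives are not inflated when neither mortality nor SpO2 differs. The problems are lost power and the mixing of mortality with oxygenation.

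For the Part 1 report, only means, SDs and CIs are affected. The change should be made, but the point does not threaten the primary endpoint.

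**What to change.** In SAP 8.2.6, keep death as the worst outcome but compare arms with a rank-based ANCOVA using the section 6.1.2 covariates. Tie all deaths below the lowest observed value, and report a rank-based effect measure with its CI. This stays within the ANCOVA approach that protocol 13.1.4.3 gives for SpO2. If the 60% ANCOVA is kept, show it only as a sensitivity analysis beside other death values, such as 50% and 70%.

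For Part 1, take 60% out of means, SDs and CIs. Report the median, range and survivors' mean, with the number dead beside them. Label the survivors' mean as descriptive, because survivors are a subset formed after randomisation. State which SpO2 tables hold observed values only, so that 8.2.6 agrees with the observed-cases tabulation in protocol 13.1.

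The cost is SAP wording and a standard procedure. The Part 2 change can go into the amendment that section 10 already foresees for the respiratory-support endpoints. The downside is that the main comparison is no longer in SpO2 points.
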